4.5.12 Nasopharyngeal Samples

Nasopharyngeal samples collected from both nostrils will be used for influenza virology tests for all patients and sent to a central laboratory. It may only be possible to access one nostril if a patient has a nasogastric tube in place, in which case sites may collect a sample from one nostril only.

Nasopharyngeal samples should be taken at screening and sent to a central laboratory **in addition** to any local swabs taken for RIDT or RT-PCR used for patient eligibility purposes. Phenotyping and genotyping will be performed according to the resistance analysis plan.

4.5.13 Endotracheal Aspirates

For patients who are intubated, endotracheal aspirates should be taken on the same day as nasopharyngeal samples (see [Appendix 1](#)), in accordance with local techniques for endotracheal aspiration. If bronchoalveolar lavage is being performed for reasons not related to the study, samples should also be collected for influenza RT-PCR assessment, if possible, for central laboratory testing.

4.5.14 Meals

Study treatment can be taken with or without food. The time of last food intake prior to each study treatment on Days 1, 4, and 7 (if additional treatment administered on Day 7) as well as the fasting period after each study treatment intake will be recorded in the eCRF.

It is recommended that dairy products and calcium-fortified beverages should not be taken with baloxavir marboxil, where possible. (see Section [4.4.2](#)).

4.5.15 Palatability and Acceptability Assessment

Patients that are awake, compos mentis, and take the study treatment (baloxavir marboxil or matching placebo) oral suspension will be asked to assess palatability and acceptability through a questionnaire ([Appendix 5](#)). The time of assessment completion should be approximately 1 minute after swallowing the study treatment solution, and before rinsing the mouth, on Day 1 and Day 4 (as well as Day 7 if an additional dose is required).

4.5.16 Ordinal Scale Determination

Assessment of patient status using an ordinal scale will be recorded at baseline on Day 1, and again once daily every morning (between 8 am and 12 pm) while hospitalized. The ordinal scale categories are as follows:

1. Discharged (or “ready for discharge”)
2. Non-ICU hospital ward (or “ready for hospital ward”) not requiring supplemental oxygen/non-invasive ventilation
3. Non-ICU hospital ward (or “ready for hospital ward”) requiring supplemental oxygen/non-invasive ventilation
4. ICU without mechanical (invasive) ventilation (or “ready for ICU admission”)
5. Mechanical (invasive) ventilation
6. Death

Patients who are ready to be discharged (e.g., still hospitalized due to non-medical or administrative reasons) will be assigned an ordinal scale of 1

Patients in non-ICU hospital ward that are eligible for ICU care based on clinical presentation but awaiting ICU care will be assigned an ordinal scale of 4.

Patients in ICU for administrative or non-medical reasons, who are ready for a non-ICU hospital ward, will be assigned an ordinal scale of 2 (if not requiring supplemental oxygen/ non-invasive ventilation) or 3 (requiring supplemental oxygen/ non-invasive ventilation).

4.6 TREATMENT, PATIENT, STUDY, AND SITE DISCONTINUATION

4.6.1 Study Treatment Discontinuation

Patients must permanently discontinue study treatment if they experience any of the following:

- Any medical condition that the investigator or Sponsor determines may jeopardize the patient’s safety if he or she continues to receive study treatment
- Investigator or Sponsor determines it is in the best interest of the patient
- Abnormal liver function test results (please refer to [Appendix 4](#))
- *Anaphylaxis or other form of hypersensitivity reaction*
- Pregnancy

The primary reason for study treatment discontinuation should be documented on the appropriate eCRF. Patients who discontinue study treatment will not be replaced.

Patients who discontinue study treatment should be continued in the study and complete all scheduled study assessments/visits per protocol, where possible.

4.6.2 Patient Discontinuation from Study

Patients who discontinue *from the study* will be asked to *complete* a study discontinuation visit. *At study discontinuation, assessments per the end of study (EOS) visit should be conducted.*

Patients have the right to voluntarily withdraw from the study at any time for any reason. In addition, the investigator has the right to withdraw a patient from the study at any time. Reasons for withdrawal from the study may include, but are not limited to, the following:

- Patient withdrawal of consent
- Study termination or site closure
- Patient non-compliance, defined as failure to comply with protocol requirements as determined by the investigator or Sponsor

Every effort should be made to obtain information on patients who withdraw from the study. The primary reason for withdrawal from the study should be documented on the appropriate eCRF. If a patient requests to be withdrawn from the study, this request must be documented in the source documents and signed by the investigator. Patients who withdraw from the study will not be replaced.

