6.1 DETERMINATION OF SAMPLE SIZE

Two new factors influenced the revised sample size: 1) the revised assumption for the placebo plus NAI control-arm TTCI following blinded data review (Section 6.1.1) and 2) the faster than anticipated enrollment rate. Integration of these two factors informed a sample size readjustment to approximately 366 randomized patients. Assuming that the RT-PCR-positive rate (tested in a central laboratory) will be 75% of the randomized population and a dropout rate of 4%, the modified intent-to-treat (influenza) infected (mITTI) population will be 264 patients (i.e., 176 patients in the baloxavir marboxil group and 88 in the placebo group). The total number of randomized patients may change based on the percentage of patients who are RT-PCR positive during the study.

The total mITTI sample size of 264 patients provides at least 80% power using the Logrank Chi-Square test to detect a 31-hour difference in TTCI between treatment groups under the following assumptions: median TTCI in the placebo plus NAI group is 94 hours, 840 hours follow-up (35 days) using 5% alpha. The minimal detectable difference is expected to be around 23 hours. The alteration of the TTCI in the placebo plus NAI group to 94 hours was selected after consideration of the response rates observed in a blinded review (see Section 6.1.1) of TTCI including data from 127 patients.

The increased sample size has the consequential benefit of a larger population for safety analysis of the combination and multiple dose regimen specifically tested in this study for the severely ill hospitalized patient group.

The study power is calculated based on the primary endpoint incorporating a group sequential design (GSD) using a beta spending function with non-binding rule, to allow for one futility interim, without increasing the overall experiment-wise error rate.

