2.4 DETERMINATION OF SAMPLE SIZE

The required sample size of the modified intent-to-treat infected (mITTI) population is 264 patients (176 patients in the baloxavir marboxil group and 88 in the placebo group). It is assumed that the reverse transcriptase polymerase chain reaction (RT-PCR)–positive rate (tested in a central laboratory) will be 75% of the randomized population; hence, approximately 366 patients will be randomized to ensure an adequate number of patients in the mITTI population and to allow for a 4% dropout rate. The total number of randomized patients may change based on the percentage of patients who are RT-PCR positive during the study.

The total mITTI sample size of 264 patients provides at least 80% power using the log-rank Chi-Square test to detect a 31-hour difference in the time to clinical improvement (TTCl) between treatment groups under the following assumptions: median TTCl in the placebo plus NAI group is 94 hours, 840 hours follow-up (35 days), using an alpha of 5%, and the minimal detectable difference is 23 hours. The TTCl in the placebo plus NAI group of 94 hours was selected after consideration of the response rates observed in a blinded review of TTCl including data from 127 patients.

The study power is calculated based on the primary endpoint incorporating a group sequential design (GSD) using a beta spending function with non-binding rule, to allow for one futility interim, without increasing the overall experiment-wise error rate.

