4.5 EFFICACY ANALYSIS

Efficacy analyses will be conducted for the mITTI population. Hypothesis tests will be two-sided at the 5% significance level, unless stated otherwise.

To manage the overall type I error, the primary and key secondary endpoints will be tested sequentially. The order of testing will be as follows:

- TTCl
- Response rates of the 6-point ordinal scale at Day 7
- Time to Clinical Response

If the primary efficacy analysis hypothesis test result is not statistically significant (i.e. $p > 0.05$), the hypothesis below that result in the hierarchical chain will be considered exploratory and no claims of statistical significance will be made. The same rules apply to the next endpoint in the chain.

4.5.1 **Primary Efficacy Endpoint**

The primary efficacy objective for this study is to evaluate the efficacy of baloxavir marboxil plus a SOC NAI, compared with matching placebo plus SOC NAI based on the following endpoint:

- TTCI (defined as time from treatment start to hospital discharge or time to NEWS2 ≤ 2 and maintained for 24 hours, whichever comes first)

TTCI is calculated as per [Table 3](#).

Table 3 TTCI Calculations

TTCI based on	TTCI (hours)
NEWS2 ≤ 2 for 24 hours	date time of initial NEWS2 assessment ≤ 2 - start treatment date time
NEWS2 ≤ 2 prior to discharge*	date time of initial NEWS2 assessment ≤ 2 - start treatment date time
Hospital discharge	date time of hospital discharge - start date time of treatment

*when a patient met the NEWS2 ≤ 2 and was discharged from hospital during the 24 hour period of stability confirmation, the time of achieving TTCI was defined as the initial time at which the NEWS2 ≤ 2 and not the time of hospital discharge.

NEWS2 (National early warning score 2) is the sum of the score of each of the following assessments, as described in [Appendix 4](#): respiration rate (per minute), oxygen saturation (SpO₂%) according to scale 1 or scale 2, supplemental oxygen or room air, systolic blood pressure (mmHg), pulse rate (bpm), consciousness level, temperature (°C).

Missing data for the calculation of the NEWS2 will not be imputed for the following reasons:

1. TTCI endpoint can be met through hospital discharge.
2. The physiological components of the NEWS2 can be highly heterogeneous in the study patient population and therefore the process of imputation would not be relevant.

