Discontinuation for any reason prior to achieving a clinical improvement	Yes	last vital signs assessment prior to discontinuation
Lost to follow-up	Yes	last vital signs assessment
No clinical improvement	Yes	last vital signs assessment

TTCI= Time to clinical improvement; NEWS2= National early warning score

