For patients who are on mechanical ventilation, or in ICU without mechanical (invasive) ventilation at start of treatment the time to clinical failure is calculated as time to worsening condition i.e. for patients with ordinal scale of 4 (ICU admission without mechanical [invasive] ventilation) at start of treatment worsening is defined as a mechanical ventilation or death), for patients with ordinal scale 5 (mechanical ventilation) at start of treatment worsening defined as a death.

Intercurrent events, such as patients who are lost to follow-up, or discontinue for any reason prior to clinical failure or do not have clinical failure, will be accounted for through censoring rules, as described in [Table 9](#) below.

Table 9 Time to Clinical Failure and Censoring

Event	Censor	Date and Time
Clinical Failure (death, mechanical ventilation, or ICU admission)	No	first occurrence of death, mechanical ventilation, or ICU admission post baseline
Death	No	date of death
Discontinuation but subsequently reported death	No	date of death
Discontinuation for any reason prior to having clinical failure	Yes	censored at last vital signs assessment
Lost to follow-up	Yes	last available date
No clinical failure	Yes	last available date

Time to hospital discharge

Time to hospital discharge, in hours, is defined as the time from start of treatment to time of discharge from hospital. Patients who are lost to follow-up, die or discontinue for any reason prior to discharge or who are not discharged will be censored at the time of their last assessment or date of death, whichever is applicable, as per rules presented in [Table 10](#) below.

Table 10 Time to hospital discharge and Censoring

Event	Censor	Date and Time
Hospital discharge	No	hospital discharge
- hospital discharge to another hospital (i.e. hospital admission within 24 hours) and discontinue study on same day	Yes	hospital discharge
- hospital discharge to another hospital (i.e. hospital admission within 24 hours) and continue study	Yes	hospital discharge
- hospital discharge against medical advice (i.e. self-discharge)	Yes	hospital discharge
- all other hospital discharge	No	hospital discharge
Death prior to hospital discharge	Yes	last vital signs assessment prior to death
Discontinuation for any reason prior to hospital discharge	Yes	last vital signs assessment prior to discontinuation
Lost to follow-up	Yes	last vital signs assessment
No hospital discharge	Yes	last vital signs assessment

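### Withdrawal from the whole study for non-compliance leads to avoidable censoring of TTCI, although the outcome could often still be read from the chart; the effect is probably small and the fix is cheap.

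*Protocol*

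**What the plan says.** Protocol 4.6.2 lets the investigator withdraw a patient from the study at any time. Its non-exhaustive list of reasons includes "Patient non-compliance, defined as failure to comply with protocol requirements as determined by the investigator or Sponsor". No threshold is set. The same section asks for a discontinuation visit with the end-of-study assessments, and for efforts to obtain information on patients who withdraw. It does not name the data items or say how they would be analysed.

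Protocol 4.6.1 treats stopping the drug differently: "Patients who discontinue study treatment should be continued in the study and complete all scheduled study assessments/visits per protocol, where possible".

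The SAP then handles patients who leave the study as follows.

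- **Table 4 (TTCI).** The row "Discontinuation for any reason prior to achieving a clinical improvement" is censored at the last vital signs before discontinuation. Tables 7 (time to clinical response), 10 (time to discharge) and 11 (time to NEWS2 of 2 or less) use the same rule.
- **Table 5 (Day 7 ordinal scale).** A patient who discontinues before Day 7 has no value imputed unless the last score was Discharged or Death.
- **Table 9 (time to clinical failure).** The row "Discontinuation for any reason prior to having clinical failure" is censored at the last vital signs, but a separate row counts a death reported after discontinuation as an event.
- **Mortality at Day 7 and Day 28 (4.5.3).** Deaths are counted, with no censoring at discontinuation.

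**The concern.** Failing a protocol requirement does not stop the primary outcome from being observed. TTCI is built from ward vital signs and the discharge date, and a hospital normally holds both whether or not the patient complied with study procedures. The plan therefore allows a discretionary decision to turn an observable outcome into a censored one.

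Only patients who have not yet improved can be affected, because an event already reached is kept. Among inpatients, that group contains the slow improvers. If withdrawal is more likely for them, the censoring carries information about prognosis, which the log-rank test and the Kaplan-Meier medians assume it does not. The design also needs an event from nearly every analysed patient, so lost events cost power directly.

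**Working it through.** **Inputs.** SAP 2.4: "The total mITTI sample size of 264 patients provides at least 80% power using the log-rank Chi-Square test to detect a 31-hour difference", with "176 patients in the baloxavir marboxil group and 88 in the placebo group". Protocol 6.1: the median "in the placebo plus NAI group is 94 hours, 840 hours follow-up (35 days) using 5% alpha". SAP 4.5: "Hypothesis tests will be two-sided at the 5% significance level, unless stated otherwise". SAP 2.5.1: one non-binding futility look at about 65% of events, Lan-DeMets Pocock beta spending, bound about p = 0.077. SAP 2.4: 75% RT-PCR positive, 4% dropout. Exponential times are assumed.

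**Step 1. Reproduce the plan.**

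- Treated median = 94 − 31 = 63 h; hazard ratio for improvement = 94/63 = 1.492; ln = 0.400.
- Sample size: 366 × 0.75 = 274.5; × 0.96 = 263.5, matching 264.
- Beta spent at the look = 0.2 × ln(1 + (e − 1) × 0.65) = 0.150. Solving for 80% power with a final critical value of 1.96 gives drift 3.052 and a futility bound at one-sided p = 0.0772, matching the SAP's 0.077.
- Events needed = 3.052² / [(2/9) × 0.400²] ≈ 262, of 264 patients (99%). Without the futility look, 221 would suffice.
- Expected events over 840 h with no loss: 263.8, for power of 80.3%. If the futility rule is not followed, about 86.5%.

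The design therefore does need almost every one of the 264 to have an event.

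**Step 2. Non-selective loss.** The rates are assumptions, and all loss is taken to occur before improvement, with the futility rule followed.

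| Lost | Events, from 264 | Power | Events, from 274.5 | Power |
|---|---|---|---|---|
| 0% | 263.8 | 80.3% | 274.3 | 81.8% |
| 2% | 258.5 | 79.5% | 268.8 | 81.0% |
| 4% | 253.3 | 78.7% | 263.3 | 80.2% |
| 8% | 242.7 | 76.9% | 252.4 | 78.5% |

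The right-hand columns start before the dropout allowance is removed, at 274.5 patients. A 4% loss then leaves the stated 80% intact. If 4% withdraw at a constant rate over 35 days, most have already improved: 262.5 events remain from 264, with power of 80.1%.

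**Step 3. What else draws on the allowance.** Deaths before improvement are also censored. Protocol 1.1 cites 4% to 8% mortality in hospitalized influenza, which is 11 to 22 of 274.5 patients. The allowance is about 274.5 − 263.5 = 11.

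**Step 4. Selective loss.** Suppose a fraction of patients with true TTCI above 240 h is withdrawn at 96 h, equally in both arms. Expected slow improvers: 88 × 2^(−240/94) = 15.0 on placebo and 176 × 2^(−240/63) = 12.6 on baloxavir. Withdrawing 20% removes about 5.5 patients (2%); 40% removes about 11 (4%). Simulated unstratified log-rank test, no interim:

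- From 264: 85.5% with none withdrawn, 82.5% at 2%, 79.7% at 4%. Repeat runs gave 84–86%, 82–83% and 79–80%.
- From about 275: 86.7% with none withdrawn, 81.2% at 4%.
- Estimated hazard ratio: about 1.46 with none, 1.45 at 2%, 1.43 at 4%.

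The shift is towards no effect because slow improvers form a larger share of the placebo arm (15.0/88 = 17%) than of the baloxavir arm (12.6/176 = 7%).

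**Step 5. Do the sensitivity analyses recover the outcome?** SAP 4.5.1.1 moves censoring to Day 35, adjusts for factors related to the reasons for discontinuation, treats death as a competing event under conditions, and examines artificial support. Censoring at Day 35 keeps the patient in the risk set as never improved. None of these uses a discharge or NEWS2 event seen after withdrawal.

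**The case against.** The case against giving this much weight is substantial, and most of it stands.

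- **Allowance.** A reader might infer from the 262-of-264 figure that there is no slack beyond about 1%. That ignores the 4% dropout allowance already in the 366. Non-selective loss of 4% fits within it, unless censored deaths use it first.
- **Scope.** A reader might infer that everything observed after discontinuation is discarded on all efficacy endpoints. The documents do not support this: Table 9 counts later-reported deaths, and the mortality endpoints are not censored at discontinuation. Later ICU or ventilation events are not used, however.
- **Who is exposed.** A reader might infer that the rule mainly removes unimproved inpatients. Protocol 4.5.4 has vital signs recorded four times a day in hospital, which leaves the patient little to fail. Missed visits arise after discharge, which is normally already a TTCI event, so those withdrawals cost nothing on the primary endpoint.
- **Frequency.** No non-compliance rate is given, and the wording is permissive. The plan expects non-compliant patients to remain: SAP 4.7.6 tabulates compliance below 80% and missed doses, and Table 5 covers ongoing patients with no Day 7 score. Removing 40% of slow improvers at 96 h is an extreme case.
- **Mitigation.** The Day 35 analysis and, for the ordinal scale, the last-score-plus-one analysis probe the missing data. Blinding limits differential use between arms.

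Two things survive. Blinding does not make the censoring unrelated to prognosis within an arm. And neither the request to obtain information on withdrawn patients nor any sensitivity analysis brings a later observed TTCI event into the results.

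**Conclusion.** The point holds as a minor, inexpensive improvement. The protocol permits withdrawal from all follow-up on a discretionary ground that does not prevent observation of the outcome. For patients withdrawn before improvement, the SAP uses no later discharge or NEWS2 in any TTCI analysis. The SAP's own Table 9 shows that information reported after discontinuation can be used.

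The effect is probably small. Non-selective loss of 4% before improvement costs about 1.6 points with the futility rule followed (80.3% to 78.7%) and about 1.4 points without it (86.5% to 85.1%), before counting the allowance. Selective loss of 2% to 4%, all slow improvers, costs about 2 to 6 points without the interim, with bias towards no effect. These figures rest on exponential times, the planned medians and assumed withdrawal rates. They do not show that the stated power is wrong or that the trial would favour baloxavir.

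**What to change.** 1. In Protocol 4.6.2, state that non-compliance alone does not end outcome follow-up. Narrow the investigator's general right of withdrawal in the same way, since deleting the non-compliance item alone would leave that discretion in place. Outcome collection would then end only with withdrawn consent or study or site closure.
2. Where consent allows, continue to collect ward vital signs and NEWS2 components, ordinal score, discharge date and vital status from the chart to Day 35.
3. In SAP Tables 4, 5, 7, 9, 10 and 11, use outcomes observed after non-compliance or treatment stop. Censor, or leave missing, only when follow-up has truly ended.

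The treatment-stopping criteria in 4.6.1 stay unchanged, and the patient's right to withdraw consent is untouched. The cost is a short protocol edit, matching SAP rows, and chart abstraction for a few patients. No change in sample size is needed.

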4.6.3 Study Discontinuation

The Sponsor has the right to terminate this study at any time. Reasons for terminating the study may include, but are not limited to, the following:

- The incidence or severity of adverse events in this or other studies indicates a potential health hazard to patients
- Patient enrollment is unsatisfactory

The Sponsor will notify the investigator if the Sponsor decides to discontinue the study.

4.6.4 Site Discontinuation

The Sponsor has the right to close a site at any time. Reasons for closing a site may include, but are not limited to, the following:

- Excessively slow recruitment
- Poor protocol adherence
- Inaccurate or incomplete data recording
- Non-compliance with the International Council for Harmonisation (ICH) guideline for Good Clinical Practice
- No study activity (i.e., all patients have completed the study and all obligations have been fulfilled)

